#### **10.1.1 Adverse Events Leading to Withdrawal of Study Drug, Drug Interruption or Dose Adjustments**

A summary of incidence rates (frequencies and percentages) of TEAEs leading to withdrawal of study drug, by SOC, and Preferred Term, will be prepared for the SAF population.

A data listing of AEs leading to withdrawal of study drug will also be provided, displaying details of the events captured on the eCRF.

Similar table and listings will be presented for TEAEs leading to drug interruptions/infusion rate reductions or dose reductions.

#### **10.1.2 Serious Adverse Events**

SAE Reconciliation will be performed by the Data Manager prior to database lock according to the SAE Reconciliation Plan.

A summary of incidence rates (frequencies and percentages) of SAEs by SOC, and Preferred Term will be prepared for the SAF Population.

A data listing of SAEs will also be provided, displaying details of the event(s) captured on the eCRF.

### **10.1.3 Adverse Events of Special Interest**

The times to the first occurrence of neutropenia (CTC-grade  $\geq 3$ ), liver enzymes increases (CTC-grade  $\geq 3$ ), (hypomagnesemia (CTC-grade  $\geq 3$ ), skin reactions (SOC="Skin and subcutaneous tissue disorders"), gastrointestinal symptoms (SOC="Gastrointestinal disorders), mucositis (PT="Mucositis") and conjunctivitis (PT="Conjunctivitis") will be investigated by Kaplan-Meier methods. Patients who did not experience this AE will be censored at the Safety Follow-up visit.

Logistic regression models including the CetuGex plasma concentration after the 3rd infusion as continuous covariable will be fitted to the incidences of AEs of special interest. Separate analyses will be performed for each of the AEs. Odds ratios, the corresponding 95%-confidence intervals and the p-values of the Wald test will be presented. Moreover, sample statistics of the CetuGex plasma concentration after the 3rd infusion grouped by the occurrence of these AEs (yes/no) will be presented including p-values of the Wilcoxon rank test.

AEs of special interest will be omitted from these analyses if their overall incidence is < 5%.

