#### **4.2 Final Analysis**

No database may be locked or analyses completed until this SAP has been approved.

The database cut-off for the statistical analysis will be set to not earlier than 12 months after randomization of the last patient.

The efficacy analysis will be performed for all patients, regarding the patients still under observation as censored and applying the same rules as defined for missing assessments and loss to follow-up.

At this time, the safety analysis will be performed on all available data, including patients still under treatment.

All statistical results will be made available to Glycotope following database cut-off and compiled into the CSR. Final results associated with OS will be added to the CSR after completion of follow-up for OS which is planned for 24 months after the last patient has been randomized.

Any post-hoc, exploratory analyses completed to support planned study analyses, which were not identified in this SAP, will be documented and reported in appendices to the CSR. Any results from these unplanned analyses (post-hoc) will also be clearly identified in the text of the CSR.

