### **5. SAMPLE SIZE DETERMINATION**

Approximately 240 patients will be randomized in this study.

The log-rank test will be used to test the hypothesis that patients assigned to the CetuGEX™ arm have increased PFS compared to patients assigned to the control arm.

The sample size calculation is based on the following assumptions:

- The median PFS in the control arm is expected to be 5.6 months post randomization.
- It is expected that the median PFS in the CetuGEX™ arm can be increased to 8.4 months corresponding to a hazard ratio of 0.67.
- The overall trial duration will be approximately 36 months with an anticipated recruitment time of 24 months, anticipated treatment phase until PFS events are reached of approximately 12 months after randomization of the last patient (data

cut-off for main analysis) and ongoing follow-up for overall survival for at least 24 months after randomization of the last patient.

- Drop-outs are expected to occur at times following an exponential distribution and resulting in a drop-out rate of 10% at the cut-off for PFS analysis.
- Patients will be randomized in a 1:1 ratio.
- The overall two-sided significance level will be 0.05 and the power to be maintained 80%.

Based on these assumptions, approximately 240 patients have to be randomized to observe the required overall number of 192 events.

If the required number of events is not reached as planned after 12 months from last patient randomized, the main analysis will be postponed to obtain more events but not more than additional 6 months.

Assuming a corresponding effect on OS (hazard ratio 0.67) and a median overall survival of 10.6 months in the control group the number of survival events to be observed after a 24-months follow-up for survival will be 183.

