## 6. ANALYSIS POPULATIONS

The analysis populations will include the following:

- The intention-to-treat (ITT) population will consist of all randomized patients. The ITT population will be the primary population for the efficacy analysis.
- The safety population (SAF) will include all patients who received at least one dose of trial medication. This population will be used for safety analyses.
- The per-protocol (PP) population will consist of all ITT patients who received at least one dose of trial medication and without major protocol deviations as defined in this SAP and finally decided in a Data Review Meeting before database lock.
- For PK analyses done in all patients the pharmacokinetic (PK) population will consist of all randomized patients who have at least one evaluable post dose concentration. For the PK profile analyses patients in the PK profile group will be included in the PK profile population who had blood samples collected for PK noncompartmental profiling and who had at least one measureable CetuGEX™ antibody concentration.

In the event that a patient is randomized incorrectly or is administered the incorrect study medication, analyses of the ITT population will be based on the assigned treatment whereas all other analyses will be based on the actual treatment.

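### The 5% omission rule for adverse events of special interest counts both arms together, so a one-arm harm can lose its time-to-event and exposure-response analyses, and the count is the wrong gate for CetuGEX-only models

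*SAP*

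**What the plan says.** SAP 10.1.3 names seven adverse events of special interest: neutropenia, liver enzyme increases and hypomagnesemia (each at CTC grade 3 or higher), skin reactions and gastrointestinal symptoms (each a whole system organ class), and mucositis and conjunctivitis (each a single preferred term). It plans three analyses for each:

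- Time to first occurrence, which "will be investigated by Kaplan-Meier methods". The censoring rule is "Patients who did not experience this AE will be censored at the Safety Follow-up visit".
- "Logistic regression models including the CetuGex plasma concentration after the 3"rd infusion, fitted to the occurrence of the event.
- Sample statistics of that concentration by occurrence of the event, with a Wilcoxon test.

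The section closes with the omission rule: "AEs of special interest will be omitted from these analyses if their overall incidence is < 5" per cent. The SAP does not define overall. SAP 7.1 sets each treatment arm against the total population, so both arms pooled is the natural reading.

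The safety population is defined in SAP 6: "The safety population (SAF) will include all patients who received at least one dose of trial medication". Under SAP 4.2, at the main cut-off "the safety analysis will be performed on all available data, including patients still under treatment".

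**The concern.** A pooled threshold ignores how the cases divide. If every case is in one arm, that arm's rate can be nearly twice the threshold and the event is still omitted. This is the pattern a safety comparison most needs to display.

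The Kaplan-Meier analysis in SAP 10.1.3 is the plan's only time-to-event analysis of adverse events. It matters because treatment runs to progression or limiting toxicity, and SAP 5 expects median PFS of 8.4 v 5.6 months. The arms are therefore expected to differ in time at risk, and crude incidence cannot separate a higher risk from a longer exposure.

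The logistic and Wilcoxon analyses use CetuGEX concentration, so only CetuGEX patients can enter them. Cases on cetuximab say nothing about whether these analyses can be estimated, yet they count towards the gate.

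The censoring rule in the same section is also incomplete. Patients still on treatment at cut-off have had no Safety visit, and neither have those who died before it was due.

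**Working it through.** **Inputs.** SAP 5: "Approximately 240 patients will be randomized in this study" and "Patients will be randomized in a 1:1 ratio", hence about 120 per arm. The size of the safety population is not given. I assume 240 and show the range down to 200. The plan states no figure for the 5% rule itself.

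**The plan's own figure.** As a check on the design inputs, Schoenfeld's formula with HR = 5.6/8.4 = 0.667, two-sided alpha 0.05 and 80% power gives 4 × (1.960 + 0.842)² / (ln 0.667)² = 191 events, against 192 stated. The design reproduces.

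**Where the rule bites.** 0.05 × 240 = 12. So 12/240 = 5.00% is kept and 11/240 = 4.58% is omitted. Some omitted splits, with two-sided Fisher exact p-values:

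- 11 v 0 (9.2% v 0%): p = 0.0008
- 10 v 1 (8.3% v 0.8%): p = 0.010
- 6 v 0 (5.0% v 0%): p = 0.029

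The 11 v 0 example is omitted for any safety population of 221 or more (11/221 = 4.98%). At 220, 11 is exactly 5.0% and is kept; the largest omitted one-sided split is then 10 v 0 (p = 0.002). At 200 it is 9 v 0 (p = 0.003).

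**How often.** The chance of omission is P(X + Y ≤ 11), with X ~ Bin(120, p1) and Y ~ Bin(120, p2). The documents give no event rates, so the rates below are assumptions:

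| True rates | Expected cases, 120 × (p1 + p2) | P(omitted) |
|---|---|---|
| 6% v 1% | 8.4 | 86% |
| 8% v 1% | 10.8 | 60% |
| 10% v 1% | 13.2 | 32% |
| 12% v 1% | 15.6 | 13% |
| 15% v 1% | 19.2 | 2% |

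**The gate on the concentration analyses.** Two cases side by side:

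- 2 CetuGEX + 10 cetuximab = 12 cases, 5.0%: kept, so a logistic model with at most 2 events is fitted.
- 11 CetuGEX + 0 cetuximab = 11 cases, 4.6%: omitted, although up to 11 events were available.

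The rule admits the weaker model and blocks the more informative one.

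**Patients without a Safety visit at cut-off.** With exponential PFS, uniform accrual over 24 months and cut-off at month 36, follow-up runs from 12 to 36 months. The proportion still progression-free is (e^(−12λ) − e^(−36λ)) / (24λ), with λ = ln 2 / median.

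- CetuGEX, median 8.4, λ = 0.0825: (0.3715 − 0.0513) / 1.980 = 0.162, or 19.4 of 120.
- Cetuximab, median 5.6, λ = 0.1238: (0.2264 − 0.0116) / 2.971 = 0.072, or 8.7 of 120.

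Adding a drop-out hazard to λ of between 0.0029 (10% by month 36, −ln 0.9 / 36) and 0.0124 (10% of all patients observed to drop out by cut-off) gives about 15 to 18 v 7 to 8. All of these count progression-free patients, so they are upper bounds for patients still on treatment.

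**The case against.** A reader might infer that a one-arm harm disappears from the safety comparison altogether. The documents do not support that:

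- The safety endpoint in SAP 2.2.2 is incidence. The tables in SAP 10.1 by system organ class and preferred term, and by maximum CTC grade, are presented by treatment group with no 5% cut-off. A split of 11 v 0 would be printed there, and all events are listed.
- Neutropenia, liver enzymes and hypomagnesemia have a second route: the CTCAE-grade frequency and shift tables for laboratory values in SAP 10.2 (Tables 14.3.4.1.6 and 14.3.4.1.7), also without a cut-off.
- SAP 10.1 keeps a table of event incidence by CetuGEX concentration after the third infusion, split at the median (Table 14.3.1.6.4).
- No planned between-arm test is lost. SAP 10.1.3 names none, and Table 14.3.3.5.1 is titled Kaplan-Meier only, whereas Table 14.2.1.1 adds a log-rank test. The Fisher p-values above describe the size of an imbalance; they do not belong to a suppressed analysis. The two concentration analyses compare no arms.

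It is also fair to say that omitting sparse models is legitimate, that large one-sided harms are mostly retained (2% omission at 15% v 1%), and that the skin and gastrointestinal classes are unlikely to fall below 5%. The pooled meaning of overall is an inference, and the closing sentence could be read as covering only the concentration analyses. Data cut-off is also the obvious censoring date for patients still on treatment.

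These points limit the consequence. They do not rescue the rule. Incidence tables do not adjust for unequal time at risk, and liver enzyme increases may span several preferred terms with no other planned adverse event table that groups them. A pooled count remains the wrong test of whether a CetuGEX-only model is estimable. A censoring date left to inference should be written down.

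**Conclusion.** The point holds for the special-interest analyses in SAP 10.1.3 and no further. As written, up to 11 pooled cases in 240 remove an event from its time-to-event and exposure-response analyses regardless of the split. The event remains visible in the by-arm incidence tables and, for the laboratory-based events, in the CTCAE tables. The events exposed are the narrowly defined ones: conjunctivitis, mucositis, and the grade 3 or higher laboratory events.

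The size depends on assumptions: overall means pooled, the closing sentence covers all three analyses, the safety population is near 240, and the true rates are those shown. The chance of omission runs from 86% at 6% v 1% to 13% at 12% v 1%, so no single percentage should be quoted alone. The mismatch between the pooled gate and the CetuGEX-only models needs no assumption about rates.

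The censoring gap is real but smaller. At most about 19 CetuGEX and 9 cetuximab patients would lack a Safety visit at month 36, fewer with drop-out or discontinuation for toxicity. These figures count all progression-free patients, not those free of a given event.

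This is a cheap improvement to secondary safety analyses, worth making before database lock.

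**What to change.** Change the wording of SAP 10.1.3 in three places:

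1. Kaplan-Meier analysis: omit an event only if its incidence in the safety population is below 5% in both arms. On 120 per arm, the smallest one-sided split then kept is 6 v 0 (6/120 = 5.0%), and 11 v 0 is kept.
2. Logistic and Wilcoxon analyses: gate on the number of CetuGEX patients with a concentration value who had the event and the number who did not. A minimum such as 10 of each would serve; the exact figure is for the trial statistician to choose and state in advance.
3. Censoring: censor event-free patients at the earliest of the Safety visit, death, last contact and data cut-off.

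The cost is SAP text and possibly a few more tables with sparse events. No clinical rule, data collection or primary analysis changes.

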## **10.2 Clinical Laboratory Evaluations**

Safety laboratory data (hematology including coagulation panel, biochemistry, urinalysis) will be collected from the respective local laboratories of each involved site.

The analysis of laboratory parameters will be presented for the SAF population, separated into blood parameters (hematology, biochemistry) and urine parameters (urinalysis). All data will be listed.

For hematology and biochemistry the laboratory values will be transformed to SI values based on SI units to make laboratory parameters comparable between different local laboratories. The relevant reference ranges supplied by each laboratory will also be transformed to SI reference ranges for each laboratory.

For hematology and biochemistry variables, descriptive summaries of absolute values and changes from baseline will be presented by visit and treatment arm. Visits with less than 10 values will be omitted. The description will include two derived visits: "Last Value under Combination Therapy" and "Last Value".

Each abnormal value will be flagged to show whether it is a value below or above the reference range. For the assessment of laboratory variables, five categories will be used taking into account the investigator's assessment of clinical relevance: 'abnormal high – clinically relevant', 'abnormal high – not clinically relevant', 'within normal limits', 'abnormal low – not clinically relevant', 'abnormal low – clinically relevant'.

The assessment of laboratory variables will be tabulated by study visit for each clinical laboratory parameter by treatment arm (frequency tables). Additionally, for each laboratory parameter, shifts in assessments from Baseline to last combination therapy visit and overall last visit will be presented by treatment arm (shift tables).

If NCI-CTCAE grades are available for a clinical laboratory analyte, these will be derived according to Common Terminology Criteria for Adverse Events version 4.03 (CTCAE) and used to present additional frequency and shift tables based on NCI-CTCAE grades.

The assessment of categorical urinalysis variables (within normal limits, abnormal – not clinically significant, abnormal – clinically significant) will be tabulated by visit for each urine parameter by treatment arm (frequency tables). Additionally, for each of these urine parameters, shifts in assessments from Baseline to EOS visit will be presented by treatment arm (shift tables).

Laboratory values that are outside the reference range will also be flagged in the data listings, along with corresponding reference ranges.

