10.1.5 Follow-Up Phase

Safety Visit (28 + 2 Days After Last Infusion)

Four weeks (28 + 2 days) after the last administration of the study drug, a Safety Visit must be performed for all patients. During this visit, the following assessments will be carried out:

- Physical examination.
- Vital signs (blood pressure, heart rate and body temperature), body weight and BMI.
- 12-lead ECG
- Record ECOG performance status.
- Blood and urine sampling for safety laboratory (hematology, coagulation panel, blood chemistry and urinalysis).
- Blood sampling for assessment of immune status (only in a subset of approximately 30 patients per treatment arm).
- Blood sampling for ADA testing (only for patients receiving CetuGEX™).
- Blood sampling for PK assessments (only for patients receiving CetuGEX™).
- QoL questionnaires EORTC-QLQ-C30 and EORTC-QLQ-H&N35 (to be performed prior to any other assessments).
- Pregnancy test for female patients of childbearing potential.
- Recording of concomitant medication.
- Assessment of AEs.

The Safety Visit is identical to the Final Examination Visit for those patients who received treatment until progression of disease.

Final Examination

As soon as progression of disease is detected, a Final Examination Visit must be performed for all patients who prematurely discontinued study treatment for any other reason except progression of disease.

In case of complete study withdrawal before documented progressive disease, a Final Examination Visit should be performed at the time of premature discontinuation.

The following assessments will be performed:

- Vital signs (blood pressure, heart rate and body temperature).
- Record ECOG performance status.
- Recording of concomitant medication.
- Assessment of AEs.

For patients discontinuing study medication due to progressive disease, the 28-day Safety Visit will constitute the Final Examination.

After the Final Examination, patients will be followed-up by quarterly phone calls until death or for a maximum duration of 24 months after randomization of the last patient for assessment of overall survival. Apart from post-PD anti-tumor therapies, no concomitant medications and no AEs will be recorded after the Final Examination.

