13.4.4.2 Clinical Laboratory Evaluations

For hematology and biochemistry variables, descriptive summaries of observed values and changes from baseline will be presented by treatment arm.

Each abnormal value will be flagged to show whether it is a value below or above the reference range. For the assessment of laboratory variables, 5 categories will be used that take into account the investigator's assessment of clinical relevance: "clin. rel., above", "non-clin. rel., above", "within", "non clin. rel., below", "clin. rel., below".

The assessments of laboratory variables concerning reference ranges and clinical relevance will be tabulated by visit for each clinical laboratory parameter by treatment arm (frequency tables). Additionally, for each laboratory parameter, shifts in assessments from baseline to the last on-study value will be presented by treatment arm (shift tables).

Laboratory values that are outside the reference range will also be flagged in the data listings, along with corresponding reference ranges.

The assessment of categorical urinalysis variables will be tabulated by visit for each urine parameter by treatment arm (frequency tables). Additionally, for each of these urine

parameter shifts in assessments from baseline the last on-study value will be presented for each treatment arm (shift tables).

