13.4.4.4 Electrocardiograms and Echocardiograms

Descriptive summaries of observed values and changes from baseline will be calculated for ECG variables. QT will be corrected according to Bazett. Frequency and shift tables will be presented for the classified values of QT_c as given by the International Conference on Harmonisation (ICH)-E14, as well as for the overall clinical assessment.

For ECHO/MUGA assessments, descriptive values of observed values at baseline (“Normal”/“Abnormal [not] clinically significant”) will be presented by treatment arm.

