## 8. STUDY PATIENTS AND DEMOGRAPHICS

### 8.1 Disposition of Patients and Withdrawals

All patients who provide informed consent will be accounted for in this study.

Descriptive summaries of population data will include

- the frequency and percentage of patients in each study population, overall and by center
- the disposition of patients, including number of patients who gave informed consent for screening, number of screening failures, number of patients randomized, number of patients completing the clinical phase (EOS visit after observed progression), number of patients discontinuing treatment without preceding progression, reason for discontinuation from treatment
- study withdrawals by reason of withdrawal
- the frequency and percentage of patients in cross-sectional subgroups defined by the stratification factors at randomization
  - FcγRIIIa status (FF, FV or VV)
  - Oral cavity and oropharynx vs. other locations
  - Locally recurrent vs. metastatic disease
  - EGFR treatment naïve vs. EGFR treatment as part of multimodal therapy

and will be presented for all randomized patients, unless otherwise specified. Subgroups will also be detailed for the PP population.

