### 10.4 Electrocardiogram

The summary ECG assessment (categories: normal, abnormal – not clinically significant, abnormal – clinically significant) will be tabulated by visit (frequency tables). Additionally, shifts in assessments from baseline to EOS visit will be presented by treatment arm (shift tables).

Descriptive summaries of actual values and changes from baseline will be presented for ECG measures of PR interval, QRS interval, QT interval, QTc interval (Bazett), and HR (heart rate) by visit and treatment arm.

If not available in the clinical database, Bazett's Correction (QTcb) will be derived as follows:

$$\text{Bazett's Correction (QT}_{c_b}\text{)} \quad \text{QT}_{c_b} = \frac{QT_{msec}}{\sqrt{RR}}$$

where: Relative Rate:  $RR = 60 / \text{HR}$   
HR = heart rate obtained from ECG.

Also, the number and percentage of patients in each treatment group with QTc values 451 - 480 ms, 481 - 500 ms or >500 ms and the number and percentage of patients in each treatment group who experienced a change >30 ms or a change >60 ms will be presented by visit.

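### The SAP ends the urinalysis and ECG shift tables at an undefined EOS visit, where the protocol ends the urinalysis shift at the last on-study value; patients with collected results can fall out of both tables.

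*SAP*

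**What the plan says.** **Urinalysis.** Protocol 13.4.4.2 plans, for each urine parameter, "parameter shifts in assessments from baseline the last on-study value will be presented for each treatment arm (shift tables". SAP 10.2 replaces that end point: "shifts in assessments from Baseline to EOS visit will be presented by treatment arm (shift tables".

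**ECG.** Protocol 13.4.4.4 plans frequency and shift tables for the QTc classes "as well as for the overall clinical assessment", without saying where the shift ends. SAP 10.4 supplies an end point: "Additionally, shifts in assessments from baseline to EOS visit will be presented by treatment arm (shift tables".

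**Blood parameters.** SAP 10.2 runs hematology and biochemistry shifts to the last combination therapy visit and to the overall last visit, in line with the protocol.

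**What EOS is.** The SAP abbreviation list expands EOS only as end of study. The protocol has a Safety Visit and a Final Examination, but no EOS visit. The nearest thing to a definition is in SAP 8.1, which counts the "number of patients completing the clinical phase (EOS visit after observed progression".

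**Declared changes.** SAP 12 states that every planned analysis agrees with the protocol.

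**The concern.** For urinalysis the two documents give different end points and the SAP does not declare the change. For ECG there is no direct conflict, but the SAP uses one rule for blood and another for urine and ECG without giving a reason.

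The choice matters because a last on-study value exists for anyone with a post-baseline result, whereas a value at a named visit exists only if the patient reaches that visit and the test is done there. If either condition fails, the patient has no end-point value and disappears from the shift table despite having data. SAP 4.2 says the safety analysis uses all available data, including patients still under treatment; an end-of-study anchor works against that.

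What is at stake is how complete two descriptive safety tables are, and whether the programmer can build them without guessing what EOS means.

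**Working it through.** Most of this is a comparison of texts. Only the group still under observation at the cut-off can be sized.

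**Step 1. Which tables.** SAP 15.1 carries the difference into the table titles. Table 14.3.4.1.5 (blood) ends at the last visit; Tables 14.3.4.2.2 (urinalysis) and 14.3.5.2.2 (ECG) end at end of study.

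**Step 2. Which visit EOS could be.**
- *Final Examination.* SAP 8.1 ties EOS to observed progression, and protocol 10.1.5 triggers only this visit by progression: "As soon as progression of disease is detected, a Final Examination Visit must be performed for all patients who prematurely discontinued study treatment" for a reason other than progression. SAP 10.1.3 names the Safety Follow-up visit separately, which suggests EOS is something else.
- *Safety Visit.* Possible, because the SAP never defines the term.

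**Step 3. Which tests are scheduled there** (protocol 10.1.5 and the schedule of events in 18.1).

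| Patient group | Safety Visit | Final Examination |
|---|---|---|
| Treated until progression | ECG and urinalysis | Same visit, so both tests |
| Stopped for another reason | ECG and urinalysis | Vital signs, ECOG, medication and AEs only |
| Still on treatment at cut-off | Not yet reached | Not yet reached |

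If EOS is the Final Examination, the second group has no scheduled end-point value for either table. If EOS is the Safety Visit, that group is kept. The third group has no EOS value on either reading.

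**Step 4. Size of the group still progression-free at the cut-off.** Inputs from protocol 13.2 and SAP 5: median PFS 5.6 and 8.4 months, 120 patients per arm, 24 months of recruitment (taken as uniform), cut-off 12 months after the last randomization, exponential drop-out reaching 10%. A drop-out hazard of η = 0.0124 per month meets the last condition.

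With λ = ln 2 / median and r = λ + η, the fraction still at risk is

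S = [exp(−12r) − exp(−36r)] / (24r).

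- Cetuximab: λ = 0.1238, r = 0.1362. S = (0.1951 − 0.0074) / (24 × 0.1362) = 0.057, and 120 × 0.057 ≈ 7 patients.
- CetuGEX: λ = 0.0825, r = 0.0949. S = (0.3201 − 0.0328) / (24 × 0.0949) = 0.126, and 120 × 0.126 ≈ 15 patients.

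Expected PFS events are 120 × (λ/r) × (1 − S): about 103 on cetuximab and 91 on CetuGEX, 194 in all, close to the 192 the plan requires. Drop-outs come to about 24 (10% of 240), so the model agrees with the plan. About 22 patients remain (22/240 = 9%).

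These 22 are progression-free; some may already be off treatment. If EOS is the Final Examination, none of them has reached it. If it is the Safety Visit, only those still on treatment, or off it for less than about 28 days, lack it.

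**Step 5. Early stoppers.** The documents give no rate of stopping for a reason other than progression. As an assumption only, 10% to 30% of 240 would be 24 to 72 patients.

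**The case against.** The strongest reply is that the missing-test problem depends on an undefined term. The phrase in SAP 8.1 describes who counts as a completer and need not define the visit. If EOS means the Safety Visit, both tests are scheduled for early stoppers. That is fair, so the loss of early stoppers is conditional. It does not remove the urinalysis conflict or the patients still on treatment at the cut-off, and an undefined anchor is itself something to correct.

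The second reply is that little is lost. By-visit urinalysis and ECG tables, by-visit QTc classes and changes, and the listings keep the data. Protocol 10.3.6.1 and 10.3.6.2 have clinically significant laboratory changes and clinically relevant ECG abnormalities reported as adverse events. None of the class-specific effects named in SAP 2.2.2 is measured by urinalysis or ECG. This stands and limits the importance of the point.

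A reader might infer that the patients most likely to show toxicity drop out and that abnormal shifts are therefore understated. The documents do not support that. Unacceptable toxicity is only one of several reasons for stopping in protocol 8.3. Early stoppers generally stay on the regular schedule until progression, so their last on-study value may come well after the last dose, once an abnormality has resolved. A last value is not a worst value.

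A reader might also add the 24 drop-outs to the 22 and call 46 patients (19%) missing. The 24 are patients lost to PFS follow-up in the planning model. Protocol 10.1.5 asks for a Final Examination at complete withdrawal, and the model does not say which tests they would have. Neither group is the early-stopper group.

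Finally, ECOG also uses EOS (SAP 10.5), but it is recorded at the Final Examination and the protocol's statistics section plans no ECOG shift. It belongs neither to the protocol conflict nor to the missing-test problem.

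**Conclusion.** The point holds in limited form. The urinalysis end point departs from the protocol without being declared. The ECG end point is not a protocol conflict, but it has the same weakness and differs from the rule for blood parameters.

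On the better-supported reading of EOS, patients who stopped for a reason other than progression have no scheduled end-point value in Tables 14.3.4.2.2 and 14.3.5.2.2; how many is unknown. On either reading, patients still on treatment at the cut-off are absent. The plan's assumptions put about 22 of 240 progression-free then, which caps the progression-free patients still on treatment. The split of about 15 to 7 arises because the planning model gives CetuGEX longer PFS, so the absences could be uneven between arms without any difference in toxicity. These figures assume exponential PFS, uniform recruitment and the planned cut-off.

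No direction of bias can be claimed. The primary PFS analysis and adverse event reporting are unaffected.

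**What to change.** 1. In SAP 10.2, end the urinalysis shift at the last on-study post-baseline value, as protocol 13.4.4.2 states.
2. In SAP 10.4, end the ECG shift at the same point, for consistency with the blood parameters.
3. Define EOS visit in the SAP as the Safety Visit, the Final Examination, or a stated rule combining them. Other SAP derivations use the term too, including the treatment period for concomitant medication (8.3) and the hospitalization percentage (7.2).
4. Retitle Tables 14.3.4.2.2 and 14.3.5.2.2 to match.
5. List in SAP 12 any departure from the protocol that remains.

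The ECOG shift may be aligned for consistency. The cost is SAP wording and two table titles; no new data or visits are needed.
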